### **6.4 Pregnancy**

If, following initiation of the study drug, it is subsequently discovered that a study subject is pregnant or may have been pregnant at the time of study exposure, including during at least 5 half lives after product administration, the investigator must immediately notify the BMS Medical Monitor/designee of this event and complete and forward a Pregnancy Surveillance Form to BMS Designee within 24 hours of awareness of the event and in accordance with SAE reporting procedures described in [Section 6.1.1](#).

In most cases, the study drug will be permanently discontinued in an appropriate manner (eg, dose tapering if necessary for subject safety).

In the rare event that the benefit of continuing study drug is thought to outweigh the risk, after consultation with BMS, the pregnant subject may continue study drug after a thorough discussion of benefits and risk with the subject.

Protocol-required procedures for study discontinuation and follow-up must be performed on the subject unless contraindicated by pregnancy (eg, x-ray studies). Other appropriate pregnancy follow-up procedures should be considered if indicated.

The investigator must immediately notify the BMS (or designee) Medical Monitor of this event and complete and forward a Pregnancy Surveillance Form to BMS (or designee) within 24 hours of awareness of the event and in accordance with SAE reporting procedures described in [Section 6.1.1](#).

Follow-up information regarding the course of the pregnancy, including perinatal and neonatal outcome and, where applicable, offspring information must be reported on the Pregnancy Surveillance Form.

Any pregnancy that occurs in a female partner of a male study participant should be reported to BMS. Information on this pregnancy will be collected on the Pregnancy Surveillance Form.

## 6.5 Overdose

An overdose is defined as the accidental or intentional administration of any dose of a product that is considered both excessive and medically important. All occurrences of overdose must be reported as an SAE (see [Section 6.1.1](#) for reporting details.).

## 6.6 Potential Drug Induced Liver Injury (DILI)

Wherever possible, timely confirmation of initial liver-related laboratory abnormalities should occur prior to the reporting of a potential DILI event. All occurrences of potential DILIs, meeting the defined criteria, must be reported as SAEs (see [Section 6.1.1](#) for reporting details). The following definition takes into account anticipated baseline compromise of liver function in patients with HCC.

Potential drug induced liver injury is defined as:

- 1) Concurrent ALT  $\geq 10 \times$  ULN, AND
- 2) Total bilirubin  $\geq 2$  times ULN or baseline value (if elevated bilirubin at study entry), AND
- 3) No other immediately apparent possible causes of ALT elevation and hyperbilirubinemia, including, but not limited to, tumor progression, acute viral hepatitis, cholestasis, pre-existing hepatic disease or the administration of other drug(s), herbal medications and substances known to be hepatotoxic.

## 6.7 Other Safety Considerations

Any significant worsening noted during interim or final physical examinations, electrocardiogram, x-ray filming, any other potential safety assessment required or not required by protocol should also be recorded as a nonserious or serious AE, as appropriate, and reported accordingly.

## 7 DATA MONITORING COMMITTEE AND OTHER EXTERNAL COMMITTEES

### 7.1 Data Monitoring Committee

A Data Monitoring Committee (DMC) will be established to provide oversight and safety and efficacy considerations in protocol CA209459. The DMC will provide advice to the sponsor regarding actions the committee deems necessary for the continuing protection of subjects enrolled in the study. The DMC will be charged with assessing such actions in light of an acceptable benefit/risk profile for nivolumab. The DMC will act in an advisory capacity to BMS and will monitor subject safety and evaluate the available efficacy data for the study.

The BMS clinical study leadership will have responsibility for overall conduct of the study including managing the communication of study data. The group will be responsible for promptly reviewing the DMC recommendations, for providing guidance regarding the continuation or termination of the study, and for determining whether amendments to the protocol or changes to the study conduct are required. Adjudicated events will be submitted to the DMC and Health Authorities when required for review on a specified timeframe in accordance with the adjudication documentation.

Details of the DMC responsibilities and procedures will be specified in the DMC charter.

## 7.2 Blinded Radiology Review Committee

In addition to local tumor assessments, images from this study will undergo a blinded, independent central review (BICR) to assess response based on the RECIST 1.1 assessment criteria. The centrally reviewed response data will be used in the analyses of ORR, PFS, duration of objective response, and time to response. All final determinations on centrally reviewed image-based endpoints will be made based on the independent assessments for a uniform and unbiased assessment of outcome. Details of the procedures and the criteria for the central review are defined in a separate Imaging charter.

## 8 STATISTICAL CONSIDERATIONS

### 8.1 Sample Size Determination

The sample size determination of this study is based on OS comparison between subjects randomized to receive nivolumab and sorafenib. With a total of 726 subjects randomized in a 1:1 ratio to receive nivolumab or sorafenib, approximately 91.5% power will be achieved with an overall type I error 0.05. The sample size determination is based on simulation using R v3.2. Below are details of the sample size determination.

#### **General assumptions:**

- There are assumed 39% HCV-infected subjects among all randomized subjects.
- In the sorafenib arm, median OS is 10 months for non-HCV infected and 14 months for HCV infected.
- Exponential distribution is assumed for OS in each randomized arm.

Estimated cumulated enrollment of randomized subjects is available in the SAP.

#### **Sample size determination for OS**

Based on simulations under the assumptions stated above, approximately 726 subjects will be randomized and followed until at least 520 OS events are observed in order to provide 91.5% power for a hazard ratio of 0.74 with a two-sided type I error of 0.05. This accounts for a group sequential testing procedure with one interim analysis and one final analysis.

The interim analysis will be conducted when 80% OS events are observed. The alpha allocation for the interim and final analyses is based on the Lan-DeMets alpha spending function approach using an O'Brien-Fleming stopping boundary controlling for a two-sided overall type I error of 5%. The stopping boundary will depend on the actual number of deaths at the time of the interim analysis and the final analysis. However, if the interim analysis is performed exactly when 80% OS events are observed, then 0.024 alpha will be used for the interim analysis and 0.043 alpha will be used for the final analysis.

It is projected that an observed hazard ratio of 0.80 or less would result in a statistically significant improvement of nivolumab at the interim analysis of OS; and an observed hazard ratio of 0.84 or

less would result in a statistically significant improvement of nivolumab at the final analysis of OS.

### **Analysis Timing Projections**

As stated above, approximately 726 subjects will be randomized to the two treatment arms in a 1:1 ratio.

- It will take approximately 13 months to complete the randomization.
- OS interim analysis is projected to occur when there are at least 416 deaths (80% of target events) among approximately 726 randomized subjects, approximately 25 months after the first subject's randomization date (13 months for randomization and 12 months for survival follow-up).
- OS final analysis is projected to occur when there are at least 520 deaths among approximately 726 randomized subjects, approximately 33 months after the first subject's randomization date (13 months for randomization and 20 months for survival follow-up).

## **8.2 Populations for Analyses**

All analyses will be performed using the treatment group as randomized (intent-to-treat) with the exception of extent of exposure (dosing) and safety, for which the treatment group as treated will be used. If a subject is randomized to nivolumab and receives at least 1 dose of nivolumab during the study, then the subject's treatment group is considered nivolumab. Similarly, if a subject is randomized to sorafenib and receives at least 1 dose of sorafenib, then the subject's treatment group is considered sorafenib. The following population datasets will be analyzed:

- **Enrolled Subjects:** Subjects who signed an informed consent form and were registered into the IVRS.
- **Randomized Subjects:** Subjects who were randomized to any treatment group in the study. This is the dataset for analyses of study conduct, study population and efficacy.
- **Treated Subjects:** Subjects who received at least one dose of nivolumab or sorafenib. This is the dataset for analyses of exposure and safety.
- **PK Subjects:** Subjects with available serum time-concentration data from randomized subjects dosed with nivolumab.
- **PD-L1 Measurable Subjects:** Randomized subjects with a measurable PD-L1 expression result (ie, excludes indeterminate and unknown)

## **8.3 Endpoints**

### **8.3.1 Primary Endpoint**

- Overall Survival (OS)  
OS is the primary endpoint for this study. It is defined as the time from the date of randomization to the date of death due to any cause in all randomized subjects. Subjects who are alive will be censored at the last known alive dates.

### 8.3.2 Secondary Endpoint(s)

- Objective Response Rate (ORR)

ORR is defined as the proportion of subjects whose best overall response (BOR) is either a CR or PR. BOR is defined as the best response designation, as determined based on BICR-assessed tumor response according to RECIST 1.1, recorded between the date of randomization and the date of first objectively documented progression or the date of subsequent anti-cancer therapy, whichever occurs first. For subjects without documented progression or subsequent anti-cancer therapy, all available response designations will contribute to the BOR determination. For a BOR of CR or PR, the initial response assessment must be confirmed by a consecutive assessment no less than 4 weeks (28 days) later.

- Progression-Free Survival (PFS)

PFS is defined as the time from the date of randomization to the date of the first objectively documented tumor progression as assessed by BICR according to RECIST 1.1 or death due to any cause in all randomized subjects. Subjects who die without a reported prior progression and without initiation of subsequent anti-cancer therapy will be considered to have progressed on the date of their death. Subjects who did not progress or die will be censored on the date of their last tumor assessment. Subjects who did not have baseline tumor assessment will be censored on the date they were randomized. Subjects who did not have any on study tumor assessments and did not die will be censored on the date they were randomized. Subjects who started any subsequent anti-cancer therapy without a prior reported progression will be censored at the last tumor assessment prior to subsequent anti-cancer therapy.

- PD-L1 expression

The objective of evaluating the relationship between PD-L1 expression and efficacy will be measured by efficacy based on PD-L1 expression. Definition of PD-L1 expression will be described in the SAP.

## **8.4 Analyses**

### **8.4.1 Demographics and Baseline Characteristics**

Demographics and baseline laboratory results will be summarized by treatment arm as randomized using descriptive statistics for all randomized subjects.

### **8.4.2 Efficacy Analyses**

#### **8.4.2.1 Analysis of OS**

A group sequential testing procedure will be applied to OS to control the overall type I error for interim and final analyses (overall  $\alpha=0.05$ ). The distribution of OS will be compared in the two randomized arms at the interim and final analyses via a two-sided, log-rank test stratified by the stratification factors using allocated alpha based on Lan-DeMets alpha spending function with O'Brien and Fleming type of boundary. The hazard ratio and the corresponding 100x (1-adjusted alpha)% CI will be estimated in a stratified Cox proportional hazards model using randomized arm as a single covariate. The OS curves for each randomized arm will be estimated using the KM product limit method. The two-sided 95% CIs for median OS will be computed by Brookmeyer and Crowley method (using log-log transformation). In addition, survival rates at select milestones will be computed as well as the corresponding two-sided 95% CIs using the log-log transformation.

#### **8.4.2.2 Analysis of ORR**

ORR based on BICR assessment per RECIST 1.1 between the two randomized arms will be compared using a two-sided Cochran-Mantel-Haenszel (CMH) test, stratified by the stratification factors. The associated odds ratio and CI will also be calculated. ORR along with its 95% exact CI will be provided for each randomization arm. Hierarchical testing of ORR will be performed upon demonstration of superiority in OS at OS interim or final analyses for all randomized subjects.

#### **8.4.2.3 Analysis of PFS**

Hierarchical testing of PFS will be performed upon demonstration of superiority in ORR at OS interim or final analyses **for all randomized subjects**. Details of timing for the analysis and alpha allocated will be described in the SAP.

PFS will be compared using a two-sided stratified log-rank test. The hazard ratio and the corresponding two-sided CIs will be estimated in a Cox proportional hazards model using treatment as a single covariate, stratified by the stratification factors. PFS curves will be estimated using the KM product-limit method. The two-sided 95% CIs for median PFS will be computed by Brookmeyer and Crowley method (using log-log transformation). In addition, PFS rate at select milestone will be computed as well as the corresponding two-sided 95% CIs using the log-log transformation.

#### **8.4.2.4 Analysis of Association between PD-L1 Expression and Efficacy Measures**

Analyses of PD-L1 expression will be descriptive. Distribution of PD-L1 expression will be examined PD-L1-measurable subjects. Potential associations between PD-L1 expression and primary efficacy measure OS will be assessed. OS curves for each randomized arm will be estimated using the Kaplan-Meier product-limit method for each PD L1 Expression subgroup. Two-sided, 95% confidence intervals for median OS will be computed by Brookmeyer and Crowley method. If there is an indication of a meaningful association, future work will evaluate PD-L1 expression as a predictive biomarker, including selection of an optimal PD-L1 expression cut-off to classify subjects as PD-L1 positive or PD-L1 negative. Cut-off selection and validation may be conducted across studies. More detailed analysis including potential associations between PD-L1 expression and secondary efficacy measures will be described in the SAP.

#### **8.4.3 Safety Analyses**

The safety analysis will be performed in all treated subjects. Descriptive statistics of safety will be presented using National Cancer Institute (NCI) Common Terminology Criteria for Adverse Events (CTCAE) version 4.0 by treatment arm. All on-treatment AEs, drug-related AEs, SAEs and drug-related SAEs will be tabulated using worst grade per NCI CTCAE v 4.0 criteria by system organ class and preferred term. On-study lab parameters including hematology, coagulation, chemistry, liver function and renal function will be summarized using worst grade per NCI CTCAE v 4.0 criteria.

#### **8.4.4 Pharmacokinetic Analyses**

The nivolumab concentration data obtained in this study may be combined with data from other studies in the clinical development programs to develop or refine a population PK model. These models may be used to evaluate the effects of intrinsic and extrinsic covariates on the PK of nivolumab and to determine measures of individual exposure. In addition, model determined exposures may be used for exposure-response analyses. Results of population PK and exposure-response analyses will be reported separately.

#### **8.4.6 Outcomes Research Analyses**

The analysis of EQ-5D and FACT-Hep data will be performed in all randomized subjects who have an assessment at baseline (Day 1, assessment prior to administration of drug on day of first dose) and at least 1 subsequent assessment while on treatment. Questionnaire completion rate, defined as the proportion of questionnaires actually received out of the expected number, will be calculated and summarized at each assessment point.

EQ-5D data will be described by treatment group as randomized in the following ways:

- EQ-5D index scores will be summarized at each assessment time point using descriptive statistics (ie, N, mean with standard deviation and 95% CI, median, first and third quartiles, minimum, maximum).
- EQ-VAS scores will be summarized at each assessment time point using descriptive statistics (ie, N, mean with standard deviation and 95% CI, median, first and third quartiles, minimum, maximum).
- The proportion (N) of subjects reporting no, moderate, or extreme problems will be presented for each of the 5 EQ-5D dimensions at each assessment time point. Subjects with missing data will be excluded from the analysis.
- A by-subject listing of the level of problems in each dimension, corresponding EQ-5D health state (ie, 5-digit vector), EQ-5D index score, and EQ-VAS score will be provided.

FACT-Hep data will be described by treatment group as randomized in the following ways:

- FACT-Hep total scores will be summarized at each assessment time point using descriptive statistics (ie, N, mean with standard deviation and 95% CI, median, first and third quartiles, minimum, maximum).
- Changes from baseline in FACT-Hep total scores will be summarized at each post-baseline assessment time point using descriptive statistics (ie, N, mean with standard deviation and 95% CI, median, first and third quartiles, minimum, maximum).
- The proportion (N) of subjects achieving a change of  $\geq 8$  points (ie, MID) in FACT-Hep total score will be summarized at each post-baseline assessment time point.

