### **3.1.2 Treatment Phase**

The treatment phase begins with the randomization call to the IVRS. The subject is randomly assigned to one of the two treatment arms. Study treatment must begin within 3 days of randomization.

Nivolumab 240 mg IV is administered as a 30-minute IV infusion every 2 weeks. Sorafenib 400 mg is administered twice a day. Both study drugs are continued until disease progression, unacceptable toxicity, withdrawal of consent or study closure. Study assessments are to be collected as outlined in [Table 5.1-2](#) and [Table 5.1-3](#).

Nivolumab or sorafenib treatment beyond initial investigator-assessed RECIST 1.1-defined progression is permitted if the subject has investigator assessed clinical benefit and is tolerating study drug, as specified in [Section 3.1.6](#). Specific requirements for subjects treated with nivolumab and sorafenib, including dose modifications, dose delays, and treatment discontinuation criteria are described in [Sections 4.5.1](#) and [4.5.3](#), respectively.

The treatment phase ends when the subject is discontinued from study drug (see [Section 3.5](#)). Subjects will then enter the Study Follow-Up Phase.

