Pregnancy test (WOCBP only)	X	Serum or urine pregnancy test (minimum sensitivity 25 IU/L or equivalent units of HCG ) to be done at screening visit and repeated within 24 hours of first dose of study therapy
SNP Sample	X	
Urinalysis	X	
Coagulation profile	X	Include International Normalized Ratio (INR). If INR cannot be done by the local laboratory, then Prothrombin Time (PT) may be provided instead
Efficacy Assessments		
Baseline tumor imaging assessment	X	CT of the chest, CT or MRI of abdomen, and pelvis with IV contrast, including required tri-phasic CT of the liver should be performed at baseline (must be performed within 28 days prior to randomization). CT chest without contrast or MRI abdomen/pelvis is acceptable if CT is contraindicated. Modality (CT or MRI) used at baseline should be used across all imaging timepoints. Bone scan is required if clinically indicated.  MRI brain within 28 days prior to randomization for subjects with a history of brain metastasis
Other Assessments		
Tumor tissue sample (biopsy)	X	A formalin-fixed, paraffin-embedded tumor tissue (FFPET) block (preferred) or minimum of 15 unstained slides of tumor tissue (archival or recent) for biomarker evaluation must be obtained. The tissue submitted will be assessed for quality with a H&E stain (100 tumor cells) and only those subjects who have met tissue quality thresholds can be randomized.
Extent of Disease & Risk Factors	X	

Table 5.1-1: Screening Procedural Outline (CA209459)		
Procedure	Pre-Treatment (Baseline)	Notes
Clinical Drug Supplies		
Register subject in IVRS	X	A call must be made to the IVRS to register subject after signing informed consent.

Table 5.1-2: On treatment Period Procedural Outline - Nivolumab (CA209459)		
Procedure	During Treatment (Cycle = 2 weeks)  Cycle 1 - Day 1 (C1, D1), Cycle 2 - Day 1 (C2 D1), (and every cycle thereafter)	Notes
Safety Assessments		
Targeted Physical examination	X	Targeted examination must include at a minimum the following body systems, performed within 72 hours prior to dosing:  Cardiovascular Gastrointestinal Pulmonary Skin
Physical Measurements	X	Weight and ECOG performance status within 72 hrs prior to dosing.
Child-Pugh Score	X	
Vital Signs	X	Including BP, HR, temperature, and respiratory rate. Obtain vital signs within 72 hrs prior to dosing.
Adverse Events Assessment	X	
Review of Concomitant Medication	X	

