Procedure	During Treatment (Cycle = 2 weeks)  Cycle 1 - Day 1 (C1, D1), Cycle 2 - Day 1 (C2 D1), (and every cycle thereafter)	Notes
Peripheral blood mononuclear cells (PBMCs) and myeloid derived suppressor cells (MDSCs)	Cycle 1, Day 1	See sections 5.6.2.3 and 5.6.2.4 , and Table 5.6.2-1 for details
Outcomes Research Assessment		Questionnaires should be administered at the start of the visit, before the subject sees the physician and before any study related procedures are done (with the exception of procedures completed 72 hours prior to visit).
EQ-5D-3L	See Note	To be completed on Cycle 1, Day 1, then every other cycle thereafter (Cycle 3, Day 1; Cycle 5, Day 1, etc.)
FACT-Hep	See Note	To be completed on Cycle 1, Day 1, then every other cycle thereafter (Cycle 3, Day 1; Cycle 5, Day 1, etc.)
Health care resource use (HCRU)	X	
Clinical Drug Supplies		
Contact central randomization IVRS / Dispense Study Drug	X	Within 3 days from randomization, the subject must receive the first dose of study medication.  Subjects may be dosed no less than 12 days between doses.

Table 5.1-3: On treatment Period Procedural Outline - Sorafenib (CA209459)		
Procedure	During Treatment: (Cycle = 2 weeks)  Cycle 1 - Day 1 (C1, D1), Cycle 2 - Day 1 (C2 D1), (and every cycle thereafter)	Notes
Safety Assessments		
Targeted Physical examination	X	Targeted examination must include at a minimum the following body systems: Cardiovascular Gastrointestinal Pulmonary Skin
Physical Measurements	X	Weight and ECOG performance status
Child-Pugh Score	X	
Vital Signs	X	Including BP, HR, temperature, and respiratory rate. BP monitoring frequency should follow local standards of care as guided by the locally approved sorafenib product label or applicable SmPC. 
2D Echocardiogram	See note	2-D echocardiogram, performed locally as clinically indicated.
Adverse Events Assessment	X	
Review of Concomitant Medication	X	

Table 5.1-3: On treatment Period Procedural Outline - Sorafenib (CA209459)		
Procedure	During Treatment: (Cycle = 2 weeks)  Cycle 1 - Day 1 (C1, D1), Cycle 2 - Day 1 (C2 D1), (and every cycle thereafter)	Notes

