FACT-Hep	See Note	To be completed on Cycle 1, Day 1, then every other cycle thereafter

Table 5.1-3: On treatment Period Procedural Outline - Sorafenib (CA209459)		
Procedure	During Treatment: (Cycle = 2 weeks)  Cycle 1 - Day 1 (C1, D1), Cycle 2 - Day 1 (C2 D1), (and every cycle thereafter)	Notes
		Cycle 3, Day 1; Cycle 5, Day 1, etc.)
Health care resource use (HCRU)	X	
Clinical Drug Supplies		
Contact central randomization IVRS / Dispense Study Drug	X	Within 3 days from randomization, the subject must receive the first dose of study medication.  IVRS should be contacted at each visit for provision of 2 week supply of sorafenib.

Table 5.1-4: Follow-Up Procedural Outline - all subjects (CA209459)			
Procedure	Follow Up, Visits 1 and 2 (X visits)a	Survival Follow Up Visits (Y visits)b	Notes
Safety Assessments			
Targeted Physical examination	X		Targeted examination must include at a minimum the following body systems: Cardiovascular Gastrointestinal Pulmonary Skin
Adverse Events Assessment	X	X	
Review of Concomitant Medications	X		
Review of Subsequent Cancer Therapy	X	X	
Laboratory Tests	X		Performed locally: CBC w/differential and platelet count, LFTs (ALT, AST, total bilirubin, alkaline phosphatase), alpha fetoprotein (AFP), BUN or serum urea level, albumin, creatinine, Ca+, Mg++, Na+, K+, Cl-, LDH, amylase, lipase, glucose, TSH (Reflex to free T3 and free T4 if TSH abnormal. Total T3/T4 are acceptable if free T3/T4 are not available.) To be done at FU1. To be repeated at FU2 if study related toxicity persists.
Pregnancy Test (WOCBP only)	X		Serum or urine pregnancy test (minimum sensitivity 25 IU/L or equivalent units of HCG).

Table 5.1-4: Follow-Up Procedural Outline - all subjects (CA209459)			
Procedure	Follow Up, Visits 1 and 2 (X visits)a	Survival Follow Up Visits (Y visits)b	Notes
Coagulation profile	X		Include International Normalized Ratio (INR). If INR cannot be done by the local laboratory, then Prothrombin Time (PT) may be provided instead
Efficacy Assessments			

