## **5.7 Outcomes Research Assessments**

Subjects will be asked to complete the EQ-5D-3L and Functional Assessment of Cancer Therapy-Hepatobiliary (FACT-Hep) questionnaire, before any clinical activities are performed during on-study clinic visits and at designated visits during the follow-up phase. The questionnaires will be provided in the subject's preferred language and may be administered by telephone during the follow-up phase. A standardized script will be used to facilitate telephone administration of the EQ-5D. A similar script does not exist for the FACT-Hep, though subjects will be provided with a hard copy of the FACT-Hep to take home and use as a visual aid during telephone interviews. [Table 5.1-1](#), [Table 5.1-2](#), [Table 5.1-3](#) and [Table 5.1-4](#) provide information regarding the timing of patient-reported outcomes assessments.

Subjects' reports of general health status will be measured using the EQ-5D. These data will be collected to assess the impact of nivolumab on generic health status and may be used to inform economic evaluations of nivolumab for the treatment of HCC.

The EQ-5D is a standardized instrument used to measure self-reports of health status and functioning. The instrument's descriptive system consists of 5 dimensions: mobility, self-care, usual activities, pain/discomfort, and anxiety/depression. Each dimension has 3 levels, reflecting "no health problems," "moderate health problems," and "extreme health problems." A dimension for which there are no problems is said to be at level 1, while a dimension for which there are extreme problems is said to be at level 3. Thus, the vectors 11111 and 33333 represent the best health state and the worst health state, respectively, described by the EQ-5D. Altogether, the instrument describes  $3^5 = 243$  health states. Empirically derived weights can be applied to an individual's responses to the EQ-5D descriptive system to generate an index measuring the value to society of his or her current health. Such preference-weighting systems have been developed for the UK, US, Spain, Germany, and numerous other populations. In addition, the EQ-5D includes a visual analog scale that allows respondents to rate their own current health on a 101-point scale ranging from "best imaginable" to "worst imaginable" health.

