2.3 Blinding and Unblinding

This is an open-label study.

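### In this open-label trial the baseline FACT-Hep and EQ-5D-3L are first completed on Cycle 1 Day 1, after randomization, so a reaction to the allocation can enter the baseline and distort the FACT-Hep change scores

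*Protocol*

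**What the plan says.** The order of events has to be assembled from several sections.

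- **Masking.** SAP 2.3: "This is an open-label study". Protocol 4.6 marks blinding as not applicable.
- **Randomization and first dose.** Protocol 3.1.2: "The treatment phase begins with the randomization call to the IVRS", and "Study treatment must begin within 3 days of randomization".
- **First questionnaire.** The on-treatment schedules, Table 5.1-2 (nivolumab) and Table 5.1-3 (sorafenib), carry the same note for EQ-5D-3L and FACT-Hep: "To be completed on Cycle 1, Day 1, then every other cycle thereafter".
- **Screening.** Table 5.1-1 has no row for either instrument. Its last row concerns registration: "A call must be made to the IVRS to register subject after signing informed consent".
- **Cross-reference.** Protocol 5.7 lists Table 5.1-1 among the tables that "provide information regarding the timing of patient-reported outcomes assessments", but that table gives no such timing.
- **Baseline.** Protocol 8.4.6 fixes it as "baseline (Day 1, assessment prior to administration of drug on day of first dose".
- **Use of baseline.** Section 8.4.6 plans FACT-Hep total scores by visit, change from baseline in the total, and the proportion with a change of at least 8 points. EQ-5D index, VAS and dimensions are summarized at each time point only.

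**The concern.** A baseline is useful for change scores because assignment cannot have influenced it. Here the only baseline follows assignment, in a trial where the subject is not masked to an infusion of a new agent or tablets of an existing one. FACT-Hep is self-reported and includes six emotional well-being items (Protocol 5.7), which could plausibly respond to hope or disappointment about the allocation.

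Randomization does not balance such a reaction, because the assignment causes it. Whatever enters the Day 1 score is subtracted, with opposite sign, from later change scores. The arm whose subjects were pleased would start higher and appear to gain less. What is at stake is how the FACT-Hep change summaries by arm are read.

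Other baselines in the protocol are tied to the period before randomization: laboratory tests within 14 days and imaging within 28 days (Table 5.1-1). The self-reported measures are the ones placed after it.

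**Working it through.** The plan states no figure on this point, so there is none to reproduce. The check covers the order of events, then what a shift would do.

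**1. Order of events**

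| Step | Source | Timing |
|---|---|---|
| Screening | Table 5.1-1 | before randomization; no questionnaire |
| Randomization call | Protocol 3.1.2 | opens the treatment phase |
| First questionnaire | Tables 5.1-2, 5.1-3 | Cycle 1 Day 1 |
| First dose | Protocol 3.1.2, 4.5; SAP 7.4.1 | within 3 days of randomization; lowest SAP category is 0 to 3 days |

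Pre-randomization assessments: 0 in both arms. If dosing follows the protocol, the baseline falls 0 to 3 days after randomization. Section 5.7 and Table 5.1-2 put questionnaires ahead of other activities at the visit. That guards against influence within the visit, but it does not place them before randomization or before the arm is disclosed.

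**2. Effect on change scores**

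Let *d* be the between-arm shift in the Day 1 score caused by knowing the arm, and *r* the fraction still present at a later visit.

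- With the Day 1 baseline, the reaction contributes *rd* − *d* = −(1 − *r*)*d* to the between-arm difference in change.
- Fades fully (*r* = 0): −*d*. Half persists (*r* = 0.5): −*d*/2. Persists unchanged (*r* = 1): 0.

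The distortion is therefore at most *d*, for *r* between 0 and 1. The documents give neither *d* nor *r*.

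**3. Illustration for the 8-point proportion**

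Assumptions, none from the documents: the change score is normal; its SD is 15, 20 or 25; mean change is 0 without a shift; the change is read as improvement (8.4.6 does not state a direction). With net shift *s* = (1 − *r*)*d*, P(change ≥ 8) = 1 − Φ((8 − *s*)/SD).

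| SD | *s* = 0 | *s* = 1 | *s* = 2 | Difference, *s* = 2 vs 0 |
|---|---|---|---|---|
| 15 | 0.297 | 0.320 | 0.345 | 4.8 points |
| 20 | 0.345 | 0.363 | 0.382 | 3.7 points |
| 25 | 0.374 | 0.390 | 0.405 | 3.1 points |

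A 2-point Day 1 shift that fades fully moves the proportion by about 3 to 5 percentage points. If half persists (*s* = 1), the movement is about 1.5 to 2.4 points.

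**4. Could the Day 1 summary reveal it?**

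With 363 per arm, full completion and a Day 1 SD also assumed to be 15 to 25, the 95% half-width for the difference in means is 1.96 × SD × √(2/363) = 2.2 to 3.6 points. A 2-point shift could not be told from chance imbalance.

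**The case against.** The strongest reply is that later scores are also given by subjects who know their arm. If the reaction persists unchanged, it cancels in a Day 1 change score, whereas a pre-randomization baseline would leave *rd* in the contrast; for *r* above one half that is more than (1 − *r*)*d*. This stands as a limit: the fix does not remove open-label reporting bias. It does not favor the Day 1 baseline, because complete cancellation needs a reaction that never changes. With a pre-randomization baseline, missing data aside, the change contrast has the same expectation as the by-visit contrast. With the Day 1 baseline the two differ by an unknown *d*.

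The 2-point illustration may also be generous. The emotional well-being items are 6 of 45 (7 + 7 + 6 + 7 + 18), worth 24 of 180 points, and Protocol 5.7 puts that subscale's minimally important difference at 2 to 3 points. A 2-point shift carried by those items alone would already reach it. This stands.

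A reader might infer stronger claims that the documents do not support:

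- *That every baseline is given in knowledge of the arm.* The documents do not say when subjects are told. Same-day dosing is possible and questionnaires come first at the visit, so some may answer before hearing. No rule secures this.
- *That EQ-5D change scores are distorted.* Section 8.4.6 plans none.
- *That the full* d *biases every later visit.* That requires the reaction to be gone by each of those visits.
- *That nothing can be salvaged.* Planned by-visit scores do not use the baseline, and Day 1 scores will be shown by arm, although step 4 shows how weak that check is.

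Parts of the SAP contents list are blanked, so any further questionnaire analysis there cannot be seen.

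**Conclusion.** The point holds in a limited form. The only baseline for both instruments is post-randomization in an open-label trial, and no rule keeps it ahead of disclosure of the arm. The analyses exposed are the FACT-Hep total change from baseline and the proportion with a change of at least 8 points; for EQ-5D, only the baseline summary is.

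Size and direction are unknown. The 3 to 5 percentage points rest on an assumed 2-point shift, an assumed SD of 15 to 25, normality, and a reaction that fades fully. They show scale and do not estimate the bias.

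The consequence is modest. These summaries are descriptive, and SAP 7.1 and 7.5.4.2 confine formal testing to OS, ORR and PFS, so no confirmatory conclusion is affected. This is a cheap improvement to the design and a limitation to disclose. Separately, the reference in Protocol 5.7 to Table 5.1-1 needs reconciling.

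**What to change.** **Design.** Add EQ-5D-3L and FACT-Hep rows to Table 5.1-1, to be completed after consent and before the randomization call, within the 14-day window already used for screening laboratory tests. Define that score as baseline in 8.4.6. Label any Day 1 questionnaire as a post-randomization time point. The reference in 5.7 then becomes correct.

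**Cost.** Two table rows and one definition, with no new visit. Some subjects who are never randomized would complete questionnaires: at most about 908 − 726 = 182 on the protocol's projections. The baseline would be up to about 2 weeks older, a real but small loss of currency in this population.

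**Data already collected.** SAP 7.10.1.1 records that enrollment was complete, so the schedule cannot help these subjects. The report should show Day 1 scores by arm, state that baseline was post-randomization and open label, and give by-visit scores equal prominence with change scores. This needs no new data.
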